***A priori* features in the primary model**

This *a priori* list of predictors will be used for the primary modeling in Objective 1: duration hypotension (summarized as a percentage of duration of MAP<75 mmHg in the duration of time modeled, e.g. postoperative day 0, 1, and 2), age, sex, emergency surgery, RCRI, and postoperative GFR, as well as the postoperative day and the interaction between postoperative day and % duration MAP<75mmHg as detailed below.

Statistical analysis

Missing data

We will exclude patients with no intraoperative or postoperative vital signs and no troponin measurements from the cohort. Complete case analysis will be performed for vital sign features, with each complete case defined as a patient with ≥ 1 vital sign measurement(s) and ≥ 1 troponin measurement(s). Since the frequencies of measurements are different, missing vital signs are not considered missing values for inclusion/exclusion purposes as long as patients meet the complete case criteria. No imputation will be performed for vital sign data.

For features that are not vital signs (e.g. age, sex), we anticipate minimal missing data (as these variables are routinely collected), and assume missing at random. Due to the longitudinal data structure with correlated observations, we opted for a simpler method of imputation for the primary analysis. For features missing $< 1\%$, complete case analysis will be

performed; between 1-<10%, multiple imputation; above 10%, the feature would be excluded from the model and the reason for missing data will be investigated.

Data quality

The data quality of the CIHI vs. chart review results of the comorbidity information will be assessed by Pearson correlation, with chart review as the gold standard.

Cohort characteristics

Continuous data will be presented in mean (SD) if normal, and median (IQR) if non-normally distributed. Categorical data will be presented as frequency (%). The following characteristics will be presented as overall group, and stratified by MINS vs. no MINS:

- Age
- Gender
- American Society of Anesthesiologists' physical status classification (ASA)
- Type of anesthesia (general, neuraxial, peripheral, and/or sedation)
- RCRI score and categories: pre-existing TIA/CVA, insulin dependent diabetes, serum creatinine >177 mmol/L, coronary artery disease, congestive heart failure, and high risk surgery including intrathoracic, intraabdominal or suprainguinal vascular surgery

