The primary analysis will involve building a linear mixed effects model (with random intercepts) to predict the maximum daily troponin level between postoperative days 0 to 2 as the continuous outcome. The postoperative days 0, 1, and 2 accounts for approximately 40%, 40%, and 10% of MINS, respectively (4). Due to the limitations in retrospective data and the daily troponin monitoring, we will use day as a unit for time rather than hour to avoid overestimation of precision by readers.

For the primary and secondary models described in Objectives 1 and 2, an *a priori* list of predictors will be used: duration hypotension (summarized as a percentage of duration of MAP<75 mmHg in the duration of time modeled, e.g. postoperative day 1) age, sex, emergency surgery, RCRI, and postoperative GFR, as well as the postoperative day and the interaction between postoperative day and % duration MAP<75 mmHg as detailed below.

For longitudinal modeling, the vital signs data and troponin data will be aggregated to the day level, so that the model can predict at the daily temporal level. If there are multiple troponin measurements on the same day, the maximum will be taken. This aggregation of the data is necessary to account for the fact that the vital signs and troponin measurements are measured at irregular intervals (both across patients and data types), often due to the acting physician's response to the patient's condition. Additionally, due to this characteristic of the raw data, the vital signs predictors will be created such that they are standardized to be robust to the number of daily measurements performed (for example, by taking the percentage of day duration, NOT the total duration, of blood pressure below a specific threshold across all measurements during that day). A categorical time variable (representing the day of the measurement) will be included as a predictor within the model.

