- Modelling using a generalized linear mixed effects model for binary definitions of troponin increase (per AHA, as described above).
 - Different truncations of vital sign data stream prior to MINS diagnosis (e.g. no truncation, 12h before diagnosis)
 - If sample size allows: subgroup analysis involving only patients with preoperative troponin; subgroup analysis for patients who are in the intensive care unit perioperatively, as this represents a sicker population.
- Intraoperative only, postoperative only
- Further inclusion of additional predictors (e.g. % duration of $\text{HR} > 100$) from the available vital signs data
- Exploration of the incremental value of vital signs in addition to the RCRI or NT-proBNP in predicting MINS or myocardial injury
- Inclusion of information from postoperative day 3
- Delta troponin (change from preoperative troponin) using linear contrast

Model evaluation

To validate the performance of the linear mixed effects model specified in the primary statistical analysis plan, given the longitudinal nature of the data, a repeated patient-based 5-fold cross-validation will be performed with 100 repetitions (doi:

10.1093/gigascience/gix019). Patient-based record was chosen as record-wise cross validation tends to overestimate prediction accuracy compared to subject-wise cross validation. Note that when using a linear mixed effects model to predict troponin for “new”

patients (such as those in a held-out validation set), there are no unique random effects corresponding to those patients and so we are assuming the mean response for these “new” patients. A “patient-based” approach for the cross-validation approach is performed to avoid data leakage from the training set into the validation set (i.e. a patient’s measurements could potentially be present in both the training and validation sets). To quantify predictive performance, the root mean square error (RMSE) will be computed for each repetition, and the corresponding average and standard deviation of those performance measures will be reported. Marginal (i.e. fixed effects only) and conditional (i.e. fixed and random effects) R-squared (Nakagawa and Schielzeth R-squared, doi.org/10.1111/j.2041-210x.2012.00261.x) will be calculated. For assessment of calibration, the predicted values will be averaged across all repetitions (for each actual observation), and a calibration plot will be generated along with measures of the calibration intercept and slope.

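### The rule that drops any non-vital feature with more than 10% missing makes no exception for the a priori predictors, so an observed missing percentage could decide whether the pre-specified models are fitted

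*Combined protocol and SAP*

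**What the plan says.** The Missing data section sets three tiers for features that are not vital signs. Below 1% missing, complete cases are used. The next tier is "between 1-<10%, multiple imputation". For the last tier, "above 10%, the feature would be excluded from the model and the reason for missing data will be investigated". The mechanism is stated in the same paragraph: "we anticipate minimal missing data (as these variables are routinely collected), and assume missing at random". The tiers follow a sentence explaining that, because observations within a patient are correlated, "we opted for a simpler method of imputation for the primary analysis".

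The predictor list is fixed elsewhere. The section on a priori features names, besides hypotension and day, "age, sex, emergency surgery, RCRI, and postoperative GFR". Primary Modeling repeats the commitment: "For the primary and secondary models described in Objectives 1 and 2, an *a priori* list of predictors will be used". Neither place says that the list gives way to the missing-data tiers, and the tiers do not exempt it.

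Under Secondary, Sensitivity, and Exploratory Analyses the plan also lists "Exploration of the incremental value of vital signs in addition to the RCRI or NT-proBNP" as a comparison. No other missing-data rule is given for the conventional-model analyses.

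**The concern.** If a listed predictor is missing in more than 10% of patients, one instruction says that it will be used and the other removes it. The composition of the primary model would then depend on a percentage seen only after extraction.

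The cut-off has no basis in the plan's own assumption. Under missing at random, multiple imputation is as valid at 11% as at 9%, and removal discards every value that was observed. Hypotension is the predictor under study. Dropping an established risk factor lowers predictive performance and, where that factor is correlated with low pressure, makes hypotension look more informative than it is.

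**Working it through.** **Exposure of each listed predictor.** Age, sex and surgical priority are very unlikely to be missing. RCRI has one laboratory component out of six (creatinine), drawn from a 30-day preoperative window. Postoperative GFR is the most exposed: the Data Dictionary has rows for preoperative creatinine and preoperative GFR, but none for postoperative GFR.

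**Where the line falls.** The Population section expects 750 patients, and 10% of 750 is 75.
- 74 missing: 74/750 = 9.87%, so the feature is imputed.
- 75 missing: exactly 10.0%, which no tier covers.
- 76 missing: 76/750 = 10.13%, so the feature is removed and 750 - 76 = 674 observed values are discarded.

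The chance of removal is P(X > 75) with X ~ Binomial(750, p). The true rate p is assumed, since none is given:

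| p | 8% | 9% | 10% | 11% | 12% |
|---|---|---|---|---|---|
| P(removed) | 0.02 | 0.15 | 0.47 | 0.79 | 0.95 |

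For true rates near 10%, chance largely decides which model is fitted.

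**Does anything change at 10%?** The efficiency of m imputations relative to infinitely many is 1/(1 + γ/m). With m = 20, and γ taken as the missing share:
- 9% missing: 1/(1 + 0.09/20) = 0.9955
- 11% missing: 1/(1 + 0.11/20) = 0.9945
- 40% missing: 1/(1 + 0.40/20) = 0.980

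This measures only the cost of a finite number of imputations, but it shows no break at 10%.

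**Cost of removal against imputation.** The documents give no effect sizes, so every input here is an assumption except n = 750. I used a patient-level linear model with standardised predictors and residual variance 1. The blood pressure coefficient is b_BP = 0.2. Three other predictors have coefficient 0.25 each. The affected feature has coefficient b = 0.1, 0.2 or 0.3 and correlation r = 0.2 with blood pressure.

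Outcome variance: V = 1 + b_BP² + 3(0.25²) + b² + 2·r·b_BP·b

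R-squared lost by removal: b²(1 - r²)/V

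Relative inflation of the blood pressure coefficient: r·b/b_BP

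| b | V | R-squared lost | Inflation |
|---|---|---|---|
| 0.1 | 1.246 | 0.0096/1.246 = 0.008 | 0.02/0.2 = 10% |
| 0.2 | 1.284 | 0.0384/1.284 = 0.030 | 0.04/0.2 = 20% |
| 0.3 | 1.342 | 0.0864/1.342 = 0.064 | 0.06/0.2 = 30% |

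In simulation (n = 750, 10 imputations, missingness at random depending on another predictor, shares of 12%, 25% and 40%), the out-of-sample loss from removal was about 0.007, 0.029 and 0.064. The average blood pressure coefficient after removal was about 0.22, 0.24 and 0.26, against a true 0.20. With multiple imputation the loss was between 0.0001 and 0.0011, and the coefficient stayed at about 0.20. At r = 0 the inflation formula gives zero.

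A second set-up, with the feature correlated 0.3 with two other predictors and 11-40% missing, agrees. At a partial R-squared of 0.01, 0.03, 0.05 and 0.10, out-of-sample R-squared was about 0.176, 0.192, 0.203 and 0.220 with the feature removed. With imputation it was about 0.182, 0.214, 0.241 and 0.297. The strongest case there loses 0.297 - 0.220 = 0.077.

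**Limits of the illustration.** It is not the plan's mixed model, and it assumes that the feature is available in the patients being predicted. Where it is often unavailable at the time of use, the gain from keeping it is smaller.

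**The case against.** The strongest reply is that the trigger may never occur. The plan expects little missing data, selects routinely collected features and adds manual chart review. That stands: the documents do not show that any listed predictor will exceed 10%, and a reader should not infer that removal is likely.

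A second reply is that this is a prediction model. A predictor often unmeasured in routine care is less usable, and a fixed pre-specified threshold is a conservative convention. Above 10%, missing at random also deserves scrutiny, and the plan does promise to investigate the reason. This is a fair ground for excluding exploratory features and for a sensitivity analysis. It does not explain why an observed percentage should override a list that the plan says will be used.

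Three stronger readings are tempting and are not supported:
- **That the rule makes the NT-proBNP comparison impossible.** NT-proBNP is neither an a priori predictor nor among the features named under Other candidate features, and the tiers are introduced for the primary analysis. The rule reaches it only if extended to exploratory models, and the RCRI comparison would remain even then. What stands is that either the rule applies or that comparison has no missing-data rule.
- **That the planned subgroup with preoperative troponin shows the plan expects gaps in its predictors.** Preoperative troponin is not a listed predictor, and its absence says nothing about creatinine or postoperative GFR.
- **That the damage can be stated as a loss of AUC.** The primary outcome is continuous and is judged by RMSE, R-squared and calibration, so R-squared is the relevant scale here.

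**Conclusion.** The point holds in conditional form. The plan contains a stated rule that, if triggered for a listed predictor, contradicts the commitment to the a priori list and gives a worse model than the imputation it already uses just below the threshold. Postoperative GFR is the realistic case; RCRI is less likely. Under the assumptions shown, removal costs about 0.007 to 0.065 of R-squared and inflates the blood pressure coefficient by about 10-30%, while imputation costs about 0.001 or less. The inflation depends on an assumed correlation of 0.2 between the feature and blood pressure, and the comparison depends on the plan's own missing-at-random assumption. The change is worth making because the remedy is cheap and the rule bears on the pre-specified models. The NT-proBNP matter is secondary.

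**What to change.** Replace the last tier with wording such as:

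> A priori predictors are kept and multiply imputed when 1% or more is missing, including at and above 10%. The imputation model is fitted within the training patients of each cross-validation fold, and held-out outcomes are not used to impute held-out predictors. If 10% or more is missing, the reason is investigated and a model without the feature is reported as a sensitivity analysis. If missingness is so high that missing at random is not credible (for example, most values missing), the model without the feature is reported alongside with equal prominence. Automatic exclusion above 10% applies only to features that are not a priori.

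Confining imputation to the training patients matters because Model evaluation adopts patient-based folds to prevent leakage. Imputing once on the full data with the outcome in the imputation model would reintroduce it.

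As a secondary change, exempt the exploratory NT-proBNP comparison from the exclusion rule, and compare the models with and without vital signs on the same patients.

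The cost is a paragraph of plan text and imputation repeated within folds, using a method already planned for the 1% to under 10% range. The downside is wider uncertainty and more reliance on missing at random when missingness is high; the sensitivity analysis makes that visible.

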Development and internal validation of models involving vital signs to predict troponin level and myocardial injury after noncardiac surgery: a single-centre retrospective cohort study

Introduction

The incidence of myocardial injury after noncardiac surgery (MINS) is approximately 12-15% and is associated with an increased risk of 30-day mortality (1), 1-year mortality (2), and 2-year major vascular events (3). Since more than 90% of patients with MINS are asymptomatic, routine troponin monitoring is required for detection (4). The postoperative days 0, 1, and 2 accounts for approximately 40%, 40%, and 10% of MINS, respectively (4). Presently, the Canadian Cardiovascular Society (CCS) perioperative guidelines recommend patients identified to be at risk according to the Revised Cardiac Risk Index (RCRI) and BNP/NT-proB-type Natriuretic Peptide (NT-proBNP) receive daily postoperative troponin monitoring for three days to identify MINS events (5). European and American societies have similar recommendations for troponin monitoring to detect MINS (6).

Current risk stratification models have multiple limitations (4). Most importantly, they predict an elevated risk over the postoperative period but cannot pinpoint when MINS may happen in the postoperative course given the patients' changing condition. Moreover, prescription of troponin monitoring is not universal (7), infrequent and inconsistent troponin monitoring may lead to delayed detection and management, and the rise of troponin is delayed by 3-4 hours from the time of injury (4).

Retrospective cohort studies show association amongst intraoperative and postoperative derangements in vital signs and MINS (4). Vital signs are routinely available within the electronic medical record, and may serve as objective predictors (i.e. as opposed to free text and disease names that have higher risks of misclassification and errors). Using both traditional longitudinal analysis techniques and novel methods in machine learning, we will investigate whether intraoperative and postoperative vital signs can enhance MINS surveillance by providing temporal prediction of MINS events.

Table 1. Preoperative factors studied in literature associated with MINS and/or major myocardial complication and mortality

Variable	References
Age	Goldman 1977 (8), Lee 1999 (9), Kheterpal 2009 (10), Botto 2014 (11), House 2016 (12)
Congestive heart failure	Lee 1999, Botto 2014
Coronary artery disease	Lee 1999, Kheterpal 2009, Botto 2014

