Following research ethics board approval, data will be extracted from Cerner Surginet Anesthesia (intraoperative electronic records) and Cerner PowerChart (preoperative and postoperative electronic records). The extracted data will consist of cohort characteristics (patient, anesthetic, surgical variables relevant to MINS (see Data Dictionary below), and patient vital signs with time stamps up to postoperative day 3. The time series time stamps will be transposed to have the start of surgery as 00:00, Jan 1, 2020. A manual chart review will also be performed to extract data not automatically retrieved from Cerner and Surginet (e.g. diagnoses of morbidities). We will extract relevant preoperative comorbidities, including RCRI and Charlson Comorbidity Index categories that are available to the Cerner team via CIHI with no date limit to obtain all preoperative comorbidities (please see Appendix). The Cerner, Surginet, and chart review data will then be linked by de-identified study ID and full surgery date.

Duration of data collection

Preoperative laboratory values are collected within 30 days before surgery. Preoperative vitals are collected within 24 hours before surgery. The total duration of subsequent data collection will be from the time of surgery up to postoperative day 3 (since the MINS protocol monitors for 3 days) or hospital discharge or death, whichever occurs first. Since 90% of MINS happen between postoperative days zero and two (4) and the frequency of monitoring would likely decrease by postoperative day 3, we will model troponin from postoperative day 0 to postoperative day 2 for the primary analysis to balance utility of the temporal model and prediction data quality.

Outcome

In the primary model, we will model high-sensitivity troponin (hsTnT) level as a continuous outcome, such that the model will remain useful if the troponin threshold definitions for MINS evolve.

In the secondary model, we will use the American Heart Association (AHA) definitions (6) for MINS, briefly:

1. Postoperative hsTnT 20 to <65 ng/L with an absolute increase of ≥ 5 ng/L amongst any postoperative troponins, or ≥ 65 ng/L, “attributable to a presumed ischemic mechanism (ie, supply-demand mismatch or atherothrombosis) in the absence of an overt precipitating nonischemic cause (eg, pulmonary embolism)”. The timestamp for laboratory diagnosis will be set at the time that the sample of elevated troponin was drawn.

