For generalizability and to decrease bias, we will select features that are routinely collected. Non-vital sign candidate features include age, sex, urgent/emergent procedure (for the index surgery), postoperative GFR, and comorbidities within the RCRI categories.

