The Cerner, Surginet, and chart review data will then be linked by de-identified Cerner study ID. The time series time stamps will be shifted to have the start of surgery as 00:00, Jan 1, 2020, in order to standardize the times for longitudinal modeling. Data will then be processed for removal of vital sign artefacts per the Multicentre Perioperative Outcomes Group protocol (35). To generate a final blood pressure dataset, if noninvasive blood pressure and invasive blood pressure are available during the same minute, then the measurement that is 1) not marked as artefact and 2) has a higher systolic blood pressure will be taken. Data will also be processed for calculation of RCRI, determination of the timing of MINS diagnosis, truncation of vital sign time series to the appropriate time stamp (see below), and calculation of duration under threshold of the time series to create vital sign summary variables as described in Table 4 for each postoperative day (0-<24h, 24-<48, 48-<72, and <72-96h after surgery end time). A formal chart review will also be performed to extract data not automatically retrieved from Cerner and Surginet, and verify data quality of automatically extracted comorbidities.

For modeling troponin as a continuous outcome, the vital sign time series will be truncated at the last troponin measurement within 3 days of surgery. For modeling the binary MINS outcome definitions the data will be truncated at the time of troponin laboratory diagnosis of the outcome event, postoperative day 3 (since the MINS protocol monitors for 3 days) or hospital discharge or death, whichever occurs first. All time measurements will be standardized as above in relation to the surgery start time.

Predictive Modeling Approaches

Approach I. Analysis using conventional longitudinal modeling (primary objective)

Data visualization

The initial exploratory analysis of the vital signs and troponin data involves time series visualizations and summaries to explore any potential patterns present in the data that may be associated with troponin quantiles or MINS or myocardial injury diagnosis. Spaghetti plots of the longitudinal data will be created for the outcome and vital signs variables, with lines colour-coded by troponin quantiles or MINS or myocardial injury diagnosis. Other relevant visualizations (scatterplots, boxplots, etc.) examining the associations between the troponin outcome and the vital signs variables will also be created.

Primary Modeling

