ASA	American Society of Anesthesia Physical Classification Score Score from 1 - 6 assessed by consulting anesthesiologist	Cohort characteristics

SBP	Systolic blood pressure with time stamp (day of surgery to POD3)	Potential predictors: univariate vs. multivariate time series; clinician-defined predictor variables.
MAP	Mean arterial blood pressure with time stamp (day of surgery to POD3)	Potential predictors: univariate vs. multivariate time series; clinician-defined predictor variables.
HR	Heart rate/pulse rate with time stamp (day of surgery to POD3)	Potential predictors: univariate vs. multivariate time series; clinician-defined predictor variables.
RR	Respiratory rate with time stamp (day of surgery to POD3)	Potential predictors: univariate vs. multivariate time series; clinician-defined predictor variables.
SpO2	Oxygen saturation by pulse oximetry with time stamp (day of surgery to POD3)	Potential predictors: univariate vs. multivariate time series; clinician-defined predictor variables.
RCRI	Revised cardiac risk index total score	Potential predictor of MINS
CCI	Charlson comorbidity index total score	Potential predictor of MINS
CVA	Presence of cerebrovascular disease CIHI preoperative diagnoses: G45.x, G46.x, H34.0, I60.x– I69.x 1/0 Yes/No	Potential predictor RCRI, CCI
IHD	Presence of ischemic heart disease CIHI preoperative diagnoses: I20.x, I21.x, I22.x, I24.x, I23.x, I25.x, Z95.1, Z95.5 1/0 Yes/No	Potential predictor RCRI, CCI

CHF	History of congestive heart failure CIHI preoperative diagnoses: I09.9, I11.0, I13.0, I13.2, I25.5, I42.0, I42.5–I42.9, I43.x, I50.x, P29.0 1/0 Yes/No	Potential predictor RCRI, CCI
Preoperative creatinine	Value in $\mu\text{mol}/\text{L}$	Potential predictor RCRI
Insulin use	Insulin (medium or long-acting) from medical administrative record 1/0 Yes/No	Potential predictor RCRI
CKD	CKD stage 4-5 or dialysis dependednt CIHI preoperative diagnoses: N18.3, N18.4, N18.5, Z49.0– Z49.2, Z99.2 1/0 Yes/No	Cohort demographics Potential predictor RCRI, CCI
PVD	Presence of peripheral vascular disease CIHI preoperative diagnoses: I70-I79 1/0 Yes/No	Potential predictor of MINS, CCI
Dementia	History of dementia CIHI preoperative diagnoses: F00.x-F03.x, F05.1, G30.x, G31.1 1/0 Yes/No	Potential predictor CCI
Chronic pulmonary disease	History of chronic pulmonary disease CIHI preoperative diagnoses: I27.8, I27.9, J40.x–J47.x, J60.x– J67.x, J68.4, J70.1, J70.3 1/0	Potential predictor CCI

	Yes/No	

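### Coded comorbidities are checked against chart review by Pearson correlation alone, which cannot show how many true cases the codes miss or how many coded cases are false

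*Combined protocol and SAP*

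**What the plan says.** The Data quality paragraph under Statistical analysis states that CIHI comorbidity information, compared with chart review, "will be assessed by Pearson correlation, with chart review as the gold standard". Data processing gives the purpose of the comparison: chart review is to "verify data quality of automatically extracted comorbidities".

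The Data Dictionary (Cerner extraction) records each coded comorbidity as present or absent. The cerebrovascular item, for example, reads "G45.x, G46.x, H34.0, I60.x– I69.x 1/0 Yes/No".

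The comorbidities enter the modelling through the RCRI. The a priori predictors of the primary model include "age, sex, emergency surgery, RCRI, and postoperative GFR", and Other candidate features lists "postoperative GFR, and comorbidities within the RCRI categories".

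No section plans sensitivity, specificity, predictive values or kappa. None gives a value of r that would count as adequate, or an action if r is low.

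**The concern.** Naming one source as the reference poses a directional question: of the patients who have the condition on chart review, how many do the codes find, and of the patients coded as having it, how many truly do? Pearson's r on two 1/0 variables is phi, and phi is unchanged when the two sources are swapped. The status given to chart review therefore has no effect on the result. Phi also merges missed cases and false codes into one number, and that number moves with prevalence even when coding accuracy is fixed.

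At stake is whether the check can do the job set for it. The Introduction itself warns of "free text and disease names that have higher risks of misclassification and errors", so the plan recognises misclassification as a risk. RCRI is a predictor in the primary and secondary models, and one planned analysis asks what vital signs add to RCRI or NT-proBNP. If coded components are used in the modelled RCRI, this comparison is the stated means of learning how good they are.

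**Working it through.** **Inputs.** The documents supply the statistic (Pearson), the 1/0 scale and the reference source. They give no correlation, prevalence or coding accuracy, so there is no figure of the plan's own to reproduce. All prevalence, sensitivity and specificity values below are assumptions.

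**Formulae.** With a = true positives, b = false positives, c = missed cases and d = true negatives:

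- r = phi = (ad − bc) / √[(a+b)(c+d)(a+c)(b+d)]
- PPV = a/(a+b)
- kappa = (observed agreement − chance agreement) / (1 − chance agreement)

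**Step 1: two opposite error profiles, as proportions of the cohort.**

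Profile A has prevalence 20%, sensitivity 40% and specificity 99%.
- a = 0.20 × 0.40 = 0.080; c = 0.20 × 0.60 = 0.120; b = 0.80 × 0.01 = 0.008; d = 0.80 × 0.99 = 0.792.
- r = (0.080 × 0.792 − 0.008 × 0.120) / √(0.088 × 0.912 × 0.20 × 0.80) = 0.0624 / 0.1133 = 0.551.
- PPV = 0.080/0.088 = 91%.
- Observed agreement is 0.872 and chance agreement 0.7472, so kappa = 0.1248/0.2528 = 0.49.

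Profile B has prevalence 5%, sensitivity 80% and specificity 95%.
- a = 0.05 × 0.80 = 0.040; c = 0.05 × 0.20 = 0.010; b = 0.95 × 0.05 = 0.0475; d = 0.95 × 0.95 = 0.9025.
- r = (0.040 × 0.9025 − 0.0475 × 0.010) / √(0.0875 × 0.9125 × 0.05 × 0.95) = 0.035625 / 0.06158 = 0.578.
- PPV = 0.040/0.0875 = 46%.
- Observed agreement is 0.9425 and chance agreement 0.87125, so kappa = 0.07125/0.12875 = 0.55.

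In A the codes miss 60% of cases but are usually right when present. In B they find 80% of cases, but more than half of the coded cases are false. The two correlations differ by 0.03.

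**Step 2: symmetry.** Take the planned cohort of 750.
- Chart review finds 150 cases, and the codes find 60 of them with no false codes: a = 60, b = 0, c = 90, d = 600. Then r = 36,000/√(60 × 690 × 150 × 600) = 0.59.
- Swap the sources, so that chart review finds 60 cases and the codes flag those 60 plus 90 others: a = 60, b = 90, c = 0, d = 600. Then r is again 0.59.

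Sensitivity is 40% in the first case and 100% in the second. PPV is 100% and 40%.

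**Step 3: dependence on prevalence.** With sensitivity fixed at 40% and specificity at 100%, r falls from 0.62 at prevalence 5% to 0.53 at 40%. With specificity 98%, it rises from 0.43 at prevalence 5% to 0.52 at 20%. Coding accuracy is constant within each pair.

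**Step 4: how high r can go when most cases are missed.** Phi² = (sensitivity + specificity − 1) × (PPV + NPV − 1). Where coding does better than chance, the first factor is at most the sensitivity and the second at most 1. With sensitivity below 50%, r therefore stays below √0.5 = 0.71. Over prevalence 5–40% and sensitivity 30–49%, r is 0.45–0.69 at specificity 100%, 0.41–0.62 at 99% and 0.34–0.59 at 98%.

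**The case against.** The strongest reply is that phi is not blind to error on binary items. It equals 1 only under perfect agreement, and it falls with both missed cases and false codes. That is correct, and it limits the point: r carries some information about overall agreement, but not about the kind of error.

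A reader might go further and infer that the correlation would make badly under-coded data look acceptable. The documents do not support that. They set no threshold for r, and Step 4 shows that r would be moderate at best if most cases were missed.

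A reader might also infer that RCRI or Charlson totals will be correlated, so that a coded score uniformly one point too low would give r = 1.00. The Data quality paragraph speaks only of comorbidity information and does not mention totals. The Data Dictionary row "Revised cardiac risk index total score" plans no correlation. A uniform one-point undercount is also impossible wherever a true score is 0, and a constant shift in a linearly entered score would be absorbed by the intercept.

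Third, it may be said that the models are unaffected. Only some RCRI components rest on CIHI codes: cerebrovascular disease, ischaemic heart disease and heart failure. Insulin use comes from the medication record, creatinine is a laboratory value and high-risk surgery is a separate variable. A CIHI-coded kidney disease item is also tagged RCRI, but Cohort characteristics defines that category by serum creatinine. Data sources also says "A manual chart review will also be performed to extract data not automatically retrieved from Cerner and Surginet (e.g. diagnoses of morbidities", so chart-review values may be what is modelled. This objection stands as a condition, because the source of the modelled RCRI is not stated.

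Finally, kappa is no cure. It too depends on prevalence and is symmetric, and at 0.49 and 0.55 it barely separates profiles A and B. That is accepted and shapes the fix.

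**Conclusion.** The point holds as a mismatch between the statistic and its stated purpose. With chart review as reference and 1/0 flags, Pearson's r cannot show how many true cases the codes miss or how many coded cases are false. In the worked profiles, r of 0.55 and 0.58 correspond to sensitivities of 40% and 80% and PPVs of 91% and 46%. The size of the effect rests on assumed inputs. The symmetry and the merging of the two kinds of error do not, because they are properties of phi.

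It does not follow that the modelled RCRI is under-ascertained. That would need the cerebrovascular, ischaemic heart disease and heart failure components to be taken from CIHI and to be poorly coded, and the documents establish neither. This is a supporting data-quality check, not part of the primary analysis. It is worth correcting because a better method is available from the same data.

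**What to change.** In the Data quality paragraph, replace the Pearson correlation as the accuracy measure. For each comorbidity, report the 2×2 table and the sensitivity, specificity, PPV and NPV of the CIHI code against chart review, with 95% confidence intervals. Kappa may be added as a supplement but should not carry the assessment. If RCRI or Charlson totals are also compared, report the mean difference together with weighted kappa or an intraclass correlation.

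It would also help to state how many charts are reviewed for this comparison and which source supplies the RCRI components in the models, since that decides whether coding error can reach the predictions.

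The cost is a sentence or two in the plan and slightly more analysis and reporting. No new data are needed.
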